#### Fruit and vegetable

The recommended amount of fruits and vegetables for a child is 5 servings per day.

5 servings of fruits and vegetables is about 1 1/2 cups of fruit and 2 cups of vegetables and includes all fresh, frozen and canned choices.

How sure are you that you could provide your child with 5 servings of fruits and vegetables everyday in the following situations?

How sure are you in the following situations?	Not at all sure	a little sure	sure	very sure	Extremely Sure
1. When you are too tired to make them	1	2	3	4	5
2. When your store doesn't have a good selection	1	2	3	4	5
3. When your family wants to eat junk food instead of fruits and vegetables	1	2	3	4	5
4. When you are eating out at a restaurant	1	2	3	4	5

(\* When you feel they are too expensive)

---

---

#### Perceived Stress

Circle the description that best represents how often you have felt or thought that way during the last month.

1) Been upset because of something that happened unexpectedly?	Never	Almost Never	Sometimes	Fairly Often	Very Often
2) Felt that you were unable to control the important things in your life?	Never	Almost Never	Sometimes	Fairly Often	Very Often
3) Felt nervous and — “stressed”?	Never	Almost Never	Sometimes	Fairly Often	Very Often
4) Felt confident about your ability to handle your personal problems?	Never	Almost Never	Sometimes	Fairly Often	Very Often

5) Felt that things were going your way?	Never	Almost Never	Sometimes	Fairly Often	Very Often
6) Found that you could not cope with all the things that you had to do?	Never	Almost Never	Sometimes	Fairly Often	Very Often
7) Been able to control irritations in your life?	Never	Almost Never	Sometimes	Fairly Often	Very Often
8) Felt that you were on top of things?	Never	Almost Never	Sometimes	Fairly Often	Very Often
9) Been angered because of things that were outside of your control?	Never	Almost Never	Sometimes	Fairly Often	Very Often
10) Felt difficulties were piling up so high that you could not overcome them?	Never	Almost Never	Sometimes	Fairly Often	Very Often

---

**The last set of questions ask additional questions about you.**

Are you currently:		Employed (full-time, part-time, or self-employed)
		Unemployed (looking for a job)
		Homemaker / stay at home parent or caregiver
		Full-time student
		Retired
		Unable to work (disabled)
What is the highest level of school you have completed?		8th grade or less
		Some high school, but did not graduate
		High school graduate or GED
		Some college or 2-year degree
		College graduate
		More than a college degree
		Prefer not to answer
We would like to ask you about your household income.		less than \$10,000
		\$10,000 to \$19,999
One of the things we're trying to understand is how people's income may affect their use of recreation centers and food choices.		\$20,000 to \$34,999
		\$35,000 to \$49,999
		\$50,000 to \$74,999
		\$75,000 to \$99,999
Which category best describes your annual household income?		\$100,000 or more
		Don't know / Not sure
		Prefer not to answer
Race		Black/African-American (non-Hispanic)
		Caucasian/White (non-Hispanic)
		Hispanic/Latino

Asian/Pacific Islander  
Native American Indian/Native Alaskan  
Not listed here  
Prefer not to answer

Please complete the address information form so we can mail you a token of appreciation for taking the time to complete the survey. Your name and mailing address is kept confidential and not linked to your survey answers.

First name Last name

---

Home address line 1

---

Home address line 2

---

City

---

State or province name

---

Zip/Postal Code

---

Country

---

May our research team contact you regarding future studies that you are eligible for?

Yes

No

What is your preferred method to be contacted for future studies?

Mail  
Phone  
Email  
(Check all  
that apply)

Phone Number

---

Email address

---

## APPENDIX 2. SURVEY ADMINISTRATION SCRIPT

As part of the COACH study at Vanderbilt, we are collecting information about each family's background, household and lifestyles. These questions include information about you and your family's education, income, racial and ethnic background, living situation, activities, eating patterns, rules, and parenting styles.

Please keep in mind that all of your answers are confidential and will not be shared with anyone outside the research project. There are some researchers who are outside of Vanderbilt that are a part of the larger research group that we will share some information with. We will take off your name and any other identifying information. The survey is voluntary, so you are free to decide not to answer any question that you do not want to answer. However, the study will be helped if you are able to answer all of the questions as completely as you can.

At any time, if you have questions, please feel free to ask me for help.

Please keep in mind that there are no right or wrong answers. Please answer the questions as honestly as you can.

Do you have any questions before we begin?

## APPENDIX 3: FREQUENTLY ASKED QUESTIONS

### 1. What does [WORD] mean?

NOTE: If the person is asking for a translation from English to another language or vice versa, the translator can provide. The possible acceptable translations should be written in advance.

If the person is asking about defining a word in English and is an English speaker, the data collector's response is "Whatever [WORD] means to you."

### 2. How do I answer if [PARTICIPANT DESCRIBES A SCENARIO]

Answer as best as you can. Choose the response that seems to best show your answer.

### 3. What is the reason you are asking about X?

"It helps us with the research project."

"It helps us learn about how different families respond to the program/research project."

### 4. I don't understand the question.

**NOTE:** If the person is asking for a translation from English to another language or vice versa, the translator can provide. The possible acceptable translations should be written in advance.

If the person is an English speaker and is asking the data collector to interpret or rephrase a question:

“Answer as best as you can. Choose the response that seems to best show your answer.”

## APPENDIX 4. QUESTIONNAIRE TRAINING CERTIFICATION LOG

Date of Approval: 05/02/2017

**VANDERBILT UNIVERSITY MEDICAL CENTER**

**STATISTICAL**

**ANALYSIS**

NCT03141151

Baseline characteristics were reported as mean (SD) or number (%) for categorical variables. The analysis used an intention-to-treat approach designed to test the difference in the BMI growth trajectory between children in the intervention and control groups. As specified a priori, BMI trajectory was modeled using a linear and a quadratic term, given the non-linear nature of early child growth. The original analysis used a longitudinal mixed-effects regression model with 2 levels (time nested within child), three random effects (intercept, linear, and quadratic), and an unstructured variance-covariance matrix. BMI data were assumed to be missing at random, and the model used a maximum likelihood procedure to handle missing outcome data (approximately 10% missing BMI data across all time points). Measurement time varied individually and was measured continuously as years since baseline data collection. Child gender was a covariate for the intercept. Child age and intervention condition were covariates for the intercept, linear, and quadratic terms. Intervention effectiveness was evaluated by a likelihood ratio test to determine whether the linear and quadratic intervention effects were jointly equal to zero (df=2; 0.05 level). However, because the linear term alone might be sufficient to adequately capture child BMI trajectory in this relatively short one-year timeframe, the original quadratic model fit was compared to an otherwise identical nested linear model using a likelihood ratio test and the AIC and BIC statistics. Baseline parent education, BMI, and age were then added to the final linear model as covariates for the intercept and linear terms.

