## 1. INTRODUCTION

The purpose of this procedure manual is to provide explicit and detailed instruction on how to collect anthropometric variables for Vanderbilt University's COACH Trial. COACH will collect measurements at four data collection time points – baseline (T1), 15 weeks (T2), 6 months (T3), and 12 months (T4).

All baseline anthropometric data will be collected prior to randomization. All data collection will occur between May 2017 and August 2018. The height and body mass variables collected will be used to calculate BMI ( $\text{kg}/\text{m}^2$ ).

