**Recollecting BMI**

Baseline BMI data must be collected  $\leq$  30 days (from anthropometry collection day) in order to randomize. Randomization must occur within 37 days. Data should not be collected between Days 31 and 37 unless extenuating circumstances warrant data collection during this period (must be PI approved; PI will determine if BMI must be recollected). If randomization occurs outside of the 37 day window, ALL data must be recollected.

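### Optional precision gain, not an error: the primary quadratic model estimates a free arm difference at baseline, although baseline BMI is measured before randomisation

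*Combined protocol and SAP*

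**What the plan says.** The Statistical Analysis section describes the primary analysis of child BMI as follows.

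- **Model.** "The original analysis used a longitudinal mixed-effects regression model with 2 levels", with random intercept, linear and quadratic effects and an unstructured covariance matrix, fitted by maximum likelihood.
- **Arm terms.** "Child age and intervention condition were covariates for the intercept, linear, and quadratic terms". Child gender enters on the intercept only.
- **Time origin.** Time is "measured continuously as years since baseline data collection", so the intercept is mean BMI at the baseline visit.
- **Test.** A likelihood ratio test on 2 df asks "whether the linear and quadratic intervention effects were jointly equal to zero". The arm term on the intercept is estimated but not tested.
- **Model choice.** The quadratic model is compared with a nested linear model that is the same in all other respects. Then: "Baseline parent education, BMI, and age were then added to the final linear model".

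The Anthropometrics manual fixes the order of events. Its Introduction says: "All baseline anthropometric data will be collected prior to randomization". The entry on recollecting BMI in Appendix 9 adds: "Randomization must occur within 37 days".

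Every secondary model adjusts for the baseline value of its own outcome.

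**The concern.** With time zero at the baseline visit, the intervention term on the intercept is the arm difference in mean baseline BMI. Baseline BMI precedes randomisation, so any such difference is chance. The primary model nevertheless estimates it freely, and nothing in the Statistical Analysis section sets the two baseline means equal.

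What is at stake is precision alone. If a child's baseline level is correlated with later change, a chance imbalance at baseline says something about the chance part of the observed difference in change. A model with one common baseline mean uses that information. A model with a separate baseline mean per arm does not. Using it is the same kind of low-cost gain as adjusting for a baseline value that has already been collected, which the secondary models do.

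**Working it through.** The documents give no power calculation, sample size, SD or correlation for this analysis, so there is no stated figure to reproduce. **All covariances below are assumptions.**

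**1. Formula.** Take complete data on a common visit schedule. Each child's fitted coefficients (intercept, linear, quadratic) then have covariance V = G + s²(Z'Z)⁻¹, where G is the random-effects covariance, s the residual SD and Z the matrix with columns 1, t, t². The arm effects on (linear, quadratic) have variance proportional to:

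- free baseline: V22
- common baseline: V22 - V21 V11⁻¹ V12

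The 12-month contrast is linear + quadratic at t = 1. Write F for its free-baseline variance and k for its covariance with the intercept. The proportional cut is k² / (V11 × F). It cannot be negative.

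**2. Worked example.** The visits come from the manual: baseline, 15 weeks (15/52.18 = 0.2875 years), 6 months and 12 months. Assume random-effect SDs of 1.0, 1.0 and 0.6, linear-quadratic correlation -0.5, s = 0.3, and intercept-slope correlation r with intercept-quadratic correlation -r/2.

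- s²(Z'Z)⁻¹ has diagonal 0.0854, 2.0259, 1.7296 and off-diagonals -0.3082 (intercept-linear), 0.2247 (intercept-quadratic), -1.7923 (linear-quadratic).
- V11 = 1 + 0.0854 = 1.0854.
- F = (1 + 2.0259) + (0.36 + 1.7296) + 2 × (-0.3 - 1.7923) = 0.9309.
- r = -0.3: k = (-0.3 - 0.3082) + (0.09 + 0.2247) = -0.2935. Cut = 0.0861 / (1.0854 × 0.9309) = 8.5%.
- r = 0: k = -0.3082 + 0.2247 = -0.0835. Cut = 0.0070 / 1.0104 = 0.7%.

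For the joint 2-df test against a linear effect, the required-N ratios are 0.911 and 0.993. From an assumed 80% power (noncentrality 9.63), dividing by these ratios gives power of 83.8% and 80.3%.

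**3. Wider grid.** This used information matrices with 1:1 arms and each follow-up missing with probability 0.10, in line with "approximately 10% missing BMI data across all time points". Assumed: intercept SD 1; residual SD 0.2 to 0.6; slope SD 0.5 to 1.2; quadratic SD 0.3 to 1.0; slope-quadratic correlation -0.3 or 0; intercept-quadratic correlation 0. There were 270 cells. Variance cut for the 12-month contrast, by intercept-slope correlation:

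- -0.5: median 22% (range 5.7% to 31%)
- -0.25: median 8.3% (1.8% to 15.8%)
- 0: median 1.5% (0.1% to 8.4%)
- +0.25: median 1.0%
- +0.5: median 4.2%

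Over all cells the median was 4.9%; half the cells were below 5% and none showed a loss. The maximum depends on the grid (24% and 37% in two other assumed grids), so it says little about this trial. From an assumed 80% power and a linear effect, power became 80-84% (median 81%) at zero correlation and 82-87% (median 84%) at -0.25. Moving the third visit to 7 months, the time used in the dose analysis, changed the maximum from 31.0% to 30.8%.

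**4. Validity.** In 20,000 simulations with an assumed 60 children per arm, type I error was 0.048 (free) and 0.049 (common).

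**5. If the effect is not linear.** Under six non-linear effect shapes the quadratic 2-df test lost at most 0.14% of its noncentrality. The nested linear model is different. With a common baseline its noncentrality fell in 19 of 45 cells for an effect seen only at 12 months (lowest ratio 0.94), in 13 of 45 for an early plateau (lowest 0.81), and in 29 of 45 for an early effect that fades (median ratio 0.57). The dose analysis describes an intensive phase followed by maintenance calls, so a non-linear effect is plausible.

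**6. Nesting.** A common-baseline quadratic model has arm terms on (linear, quadratic). A free-baseline linear model has them on (intercept, linear). Neither contains the other, so the planned likelihood ratio comparison would no longer apply to that pair.

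**The case against.** The strongest reply is that nothing here is wrong. Letting the arms differ at the intercept is a valid choice, and baseline BMI is already in the model as the first repeated outcome. That stands. But with a separate baseline mean per arm, including baseline as a response does not let the chance imbalance sharpen the estimated effect on change.

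Second, the analysis appears finished. The text is in the past tense, reports observed missingness and names a final linear model. This largely stands, and it limits the remedy to a sensitivity analysis.

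Third, the model carried forward appears to be linear, where the common baseline is not recommended as primary. That reduces the relevance, although the quadratic 2-df test remains the stated test of effectiveness.

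Fourth, the gain rests wholly on assumed covariances. That stands.

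Three stronger readings are tempting, and the documents do not support them:

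- A reader might infer that the primary result is biased or that its test has the wrong size. Randomisation makes the free-baseline model valid, and the simulation agrees.
- A reader might infer that the primary and secondary analyses contradict each other. They are different but coherent designs.
- A reader might infer that the final linear model already adjusts for the child's baseline BMI. The wording most naturally means the parent's BMI. In any case that step concerns the linear model and is not described as removing the arm term from the intercept.

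**Conclusion.** The point holds as an optional improvement. The stated quadratic model is valid but does not use the equality of baseline means that randomisation supplies. In large samples, and if the mean model is correct, constraining those means cannot reduce precision for the linear and quadratic intervention effects.

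The size is unknown. Under the assumed covariances the median variance cut for the 12-month contrast is about 1% to 2% at zero intercept-slope correlation and about 8% at -0.25. It may be close to zero. A reader might infer from the larger grid values that the trial lost substantial power; the documents give no sample size, BMI SD or correlation that would support this. The conclusion does not extend to the linear model, where the constraint can lose power if the effect is not linear. Confidence is medium, because the visible analysis text is a short summary and the documents do not describe the allocation method.

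**What to change.** **If outcomes have not been analysed:** remove intervention condition from the intercept of the primary quadratic model and keep it on the linear and quadratic terms, so that both arms share one baseline mean given child age and gender. Use the same 2-df likelihood ratio test and keep the free-baseline model as a sensitivity analysis.

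**If outcomes have been analysed, as the text indicates:** keep the prespecified free-baseline model as primary and report the common-baseline quadratic model as a labelled sensitivity analysis, whatever it shows. Replacing the primary model at this stage would be a post-hoc change.

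**In either case:** compare the quadratic and linear models only when both have the free baseline, so that they stay nested. Use the common baseline in the linear model only as a sensitivity analysis.

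The cost is one extra model fit and no new data. The downside is that the common-baseline result relies on the mean model being correct.
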